11.1. General

The PK Analysis Set will serve as the primary analysis set for PK analyses. The analysis will be conducted by treatment arm and dose cohort of mRNA-2416 (as specified in [Section 3.3](#)) for Phase I and Phase II.

11.2. Values Below the Limit of Quantitation or Missing

Concentration values that are below the limit of quantification (BLQ) will be set to zero, with defined exceptions as follows:

- Any embedded BLQ value (between 2 quantifiable concentrations) and BLQ values following the last quantifiable concentration in a profile will be set to missing for the purposes of PK analysis.
- If there are late positive concentration values following 2 BLQ concentration values in the apparent terminal phase, these values will be evaluated. If these values are considered to be anomalous, they will be set to missing.
- If an entire concentration-time profile is BLQ, the profile will be excluded from the PK analysis.
- If a pre-dose concentration is missing, these values may be set to zero.

11.3. Anomalous Values

If a value is considered to be anomalous due to being inconsistent with the expected PK profile, it may be appropriate to exclude this point from the PK analysis. However, the exclusion of data must have strong justification and will be documented in PK section of the Clinical Study Report.

Embedded BLQ values may be considered anomalous depending on the route of administration and the characteristics of the drug.

Positive pre-dose value(s) greater than 5% of C_{max} may be excluded from the summary statistics of PK tables and statistical analysis at the discretion of the pharmacokineticist.

11.4. Serum Concentration

Blood samples for determination of mRNA-2416 serum concentrations and durvalumab serum concentrations will be collected via venipuncture or an indwelling catheter in Cycle 1 at pre-dose (prior study drug administration), at 3, 6 and 24 (Cycle 1 Day 2) hours post-dose and at pre-dose on Cycle 1 Day 8 and Cycle 2 Day 1.

Serum concentration data of mRNA-2416 and durvalumab will be individually listed and summarized using descriptive statistics by nominal time point (n, mean, standard deviation, coefficient of variation [CV], geometric mean, median, minimum, and maximum). Geometric mean will not be calculated where the minimal concentration values include zero.

Geometric mean serum concentration by nominal time profiles by period and treatment both in linear and semi-logarithmic scale will be provided; individual serum concentration plots by actual sampling time for all patients combined within period and treatment will be provided on a linear and semi-logarithmic scale.

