7.6 EXPLORATORY ENDPOINTS

The exploratory endpoints of the study are as follows:

- Assessment of objective response rate of mRNA-2416 alone and in combination with durvalumab based on irRC or LYRIC
- Assessment of the correlation of other investigational serum-based proteins (eg, anti-drug antibodies) with PK, efficacy, and safety
- Evaluation of plasma will include assessment of pro-inflammatory cytokines and interferons
- Evaluations of tumor tissue will include:
 - Expression of OX40 and OX40L and change in expression over the treatment period
 - Expression of other immune-related markers, including PD-1 and PD-L1
 - Infiltration of tumor with immune effector cells, including T cells

- PK parameters for durvalumab in combination with mRNA-2416: maximum observed concentration and area under the concentration-time curve

The on-treatment biopsy timing may be adjusted based on emerging data.

Where possible, outcome measures will be correlated with clinical characteristics such as tumor histotype, dose of mRNA administered, and clinical outcomes.

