10.12.1 DURVALUMAB PHARMACOKINETICS

Blood samples will be collected at the time points indicated in [Table 6](#) and may be used to assess durvalumab serum concentration.

If emerging data from this study are consistent with the existing data from other durvalumab clinical trials, durvalumab PK sampling may be reduced or discontinued.

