10.13 BIOMARKERS

In this study, biomarker samples will be collected per Tables 6, 7,8 and 9. The biomarker analysis will be used to investigate the effect of mRNA-2416, as well as to determine how the markers are associated with clinical outcome. Immune responses will be studied in the peripheral circulation and in tumor biopsy specimens. Tumor biopsies will be examined using methods such as immunohistochemistry, quantitative immunofluorescence, RNA sequencing and/or electrochemiluminescence (ECL) assays to evaluate changes in key immune pathway axes, such as PD-L1/PD-1 and OX40L/OX40, as well as characterization (eg, phenotype, distribution, and activation) of tumor infiltrating lymphocyte and myeloid populations. Cytokines may also be examined in both tumor and blood tissues using methods such as RNA sequencing and enzyme-linked immunosorbent assay (ELISA)/ ECL assays, respectively.

The goal of the biomarker assessments is to provide supportive data for the clinical study; however, there may be circumstances when a decision is made to stop a collection or not perform or discontinue an assessment (eg, inadequate sample number, sample quality or assay issues that preclude analysis, or impossibility to perform correlative analyses). Therefore, sample collection and/or assessment may be omitted at the discretion of the Sponsor.

The sample collection information must be entered on the appropriate sample collection log eCRF page(s). Sample details including volume and instructions for the collection, handling, and shipment of samples are outlined in the laboratory manual for the study.

Table 6: Sampling schedule for Pharmacokinetics, Immunogenicity, and Cytokine Profiling

Cycle	Day	Scheduled Time (Sampling Window)	Purpose ^a
1	1	Pre-dose of Cycle 1 Day 1	PK, Cytokines, IG
1	1	3 h from start of injection (\pm 10 min)	PK, Cytokines
1	1	6 h from start of injection (\pm 30 min)	PK, Cytokines
1	2	24 h from start of injection (\pm 60 min)	PK, Cytokines
1	8	168 h from start of injection (\pm 24 h)	PK, Cytokines
1	15	Pre-dose of Cycle 1 Day 15	IG
2	1	Pre-dose of Cycle 2 Day 1	PK, Cytokines, IG, mAb PK
3	1	Pre-dose of Cycle 3 Day 1	IG
3	15	Pre-dose of Cycle 3 Day 15	IG
4	1	Pre-dose of Cycle 4 Day 1	IG
5	1	Pre-dose of Cycle 5 Day 1	IG
6	1	Pre-dose of Cycle 6 Day 1	IG
6	15	Pre-dose of C1D15	IG
EOT		Anytime	IG
Unscheduled		Anytime when needed	PK, Cytokines, IG, mAb PK

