Abbreviations: EOT, end of treatment; FU, follow-up; IG, immunoglobulin; PEG, polyethylene glycol, mAb, monoclonal antibody (durvalumab).

a. IG analyte is anti- PEG and -OX40L anti-drug antibody

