13.4.4 PK AND PHARMACODYNAMIC ANALYSES

mRNA-2416 and durvalumab PK parameters to be determined will include, but are not limited to, Cmax, time to maximum observed concentration, elimination half-life, and AUC. Where possible, descriptive statistics of the PK parameters will be provided; individual patient mRNA-2416 concentrations, actual sampling times, and PK parameters will be listed.

This study will assess the immunological effects of each treatment cycle on the cellular and humoral immune responses in the peripheral circulation and in tumor biopsy specimens. Humoral immune responses (potential antibody production) to the study drug will be compared to baseline in serum samples.

Tumor biopsies will be examined using immunohistochemistry, qualitative immunofluorescence and/or an orthogonal approach (i.e. ELISA) for changes in OX40L/OX40 and PD-L1/PD-1 expression levels, as well as characterization of tumor infiltrating lymphocyte populations (eg, phenotype, distribution, and activation). Plasma may be evaluated for changes in cytokine levels.

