11.5. Serum Pharmacokinetic Parameters

The individual serum concentration versus actual time data for mRNA-2416 and durvalumab will be used to derive the PK parameters using non-compartmental PK analyses with Phoenix WinNonlin version 8.0 or higher.

The following serum PK parameters will be calculated for mRNA-2416 and durvalumab if data permit:

C_{\max}	Maximum observed serum concentration, obtained directly from the observed concentration time data.
t_{\max}	Time to maximum observed serum concentration, obtained directly from the observed concentration time data.
AUC_{0-t}	AUC from 0 hour to the time of the last observed quantifiable serum concentration (C_{last}); calculated by linear up log down trapezoidal method.
$AUC_{0-\infty}$	AUC extrapolated to infinity; calculated as $[AUC_{0-t} + (C_{\text{last}}/\lambda_z)]$
%AUC	Percentage of estimated part of the calculation of $AUC_{0-\infty}$, calculated as: $((AUC_{0-\infty} - AUC_{0-t}) / AUC_{0-\infty}) \times 100$; If %AUC extrapolated is higher than 30%, then $AUC_{0-\infty}$ and parameters derived from it will be displayed in the listing (flagged) and excluded from descriptive statistics and statistical analysis.
λ_z	Apparent elimination rate constant, estimated by linear regression of the terminal portion of the log-concentration by time curve; a minimum of 3 non-BLQ data points in the elimination phase (not including C_{\max}) will be used for the calculation. The λ_z will not be estimated if adjusted r-squared is less than 0.8.
$t_{1/2}$	Apparent elimination half-life, calculated as $[(\ln 2)/\lambda_z]$. If the length of the time interval used to determine λ_z is less than 2 times $t_{1/2}$, then $t_{1/2}$ will be flagged (i.e., $t_{1/2}$ values that are more than half the time interval used to determine λ_z will be flagged).

Adjusted r-squared, number of points to calculate slope of terminal phase and start and end of the λ_z will be listed. Additional parameters may be calculated if deemed necessary.

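### SAP sections 11.4–11.5 derive durvalumab Cmax, AUC and half-life from six sampling times, but protocol Table 6 schedules one durvalumab sample, the Cycle 2 Day 1 trough

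*SAP*

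**What the plan says.** **Endpoint.** Protocol section 7.6 lists as exploratory: "PK parameters for durvalumab in combination with mRNA-2416: maximum observed concentration and area under the concentration-time curve". SAP section 3.2.3 repeats it. Protocol section 13.4.4 goes further: "mRNA-2416 and durvalumab PK parameters to be determined will include, but are not limited to, Cmax", followed by tmax, elimination half-life and AUC.

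**Sampling in the protocol.** Section 10.12.1 refers to the times in Table 6 and says the samples "may be used to assess durvalumab serum concentration". In Table 6 (section 10.13) only the pre-dose C2D1 row and the Unscheduled row read "PK, Cytokines, IG, mAb PK". The footnote expands the label: "mAb, monoclonal antibody (durvalumab". The Cycle 1 rows at pre-dose, 3, 6, 24 and 168 h carry PK without mAb PK.

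**Sampling in the SAP.** Section 11.4 opens: "Blood samples for determination of mRNA-2416 serum concentrations and durvalumab serum concentrations will be collected". It lists pre-dose, 3, 6 and 24 h, and ends "at pre-dose on Cycle 1 Day 8 and Cycle 2 Day 1". Both drugs share this one list.

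**Derivation.** SAP section 11.5 computes Cmax, tmax, AUC0-t, AUC0-∞, λz and half-life for both drugs where the data allow. Cmax is read directly from the observed values, and λz needs "a minimum of 3 non-BLQ data points in the elimination phase", not counting Cmax. SAP section 13 does not list the different sampling schedule as a change.

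**The concern.** The two documents disagree on how many durvalumab samples exist, and the SAP's analysis relies on the larger number. The protocol also disagrees with itself, because sections 7.6 and 13.4.4 call for parameters that Table 6 cannot support.

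At stake is an exploratory result that is either missing or mislabelled. Half-life and AUC0-∞ would simply fail. Cmax needs only one value, so the SAP's rules would let the trough stand as the maximum.

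A second, smaller matter comes from the same SAP list. It places the C2D1 draw in one series with the Day 1 mRNA-2416 samples, although a further mRNA-2416 dose falls on Day 15 with no PK draw around it. Cmax and AUC of mRNA-2416 are secondary endpoints; its half-life is not named as one and appears only in the analysis text.

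**Working it through.** No figure in the plan needs reproducing. The check is a count of samples, followed by the SAP's own rules.

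**1. Scheduled samples assigned to durvalumab**

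| Time | Table 6 | SAP 11.4 |
|---|---|---|
| C1D1 pre-dose | no | yes |
| 3 h | no | yes |
| 6 h | no | yes |
| 24 h | no | yes |
| C1D8 (168 h) | no | yes |
| C2D1 pre-dose | yes | yes |
| Total | 1 | 6 |

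The plain PK label cannot be stretched to cover durvalumab. The C2D1 row lists PK and mAb PK separately, and protocol section 10.12 ties the PK draws to mRNA-2416.

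**2. What one trough yields under SAP 11.5**

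- λz has 1 point available against 3 required, so λz, half-life and AUC0-∞ fail.
- Cmax becomes the Day 28 value.

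To size this I assume one-compartment decline. The half-life of about 21 days is from protocol section 6.5; the 14 to 28 day range is my assumption.

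- Trough/peak = 2^(−28/t½). At 21 days: 2^(−1.333) = 0.397. At 14 days: 0.25. At 28 days: 0.50.
- SAP section 11.2 lets a missing pre-dose value be set to zero. AUC0-t would then be a triangle. With peak = 1 and k = ln 2/21 = 0.0330 per day, the triangle is ½ × 28 × 0.397 = 5.56. The modelled AUC over 28 days is (1 − 0.397)/0.0330 = 18.3. The ratio is 0.30.

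The one-compartment model can be tested against protocol section 6.5, which reports a steady-state Cmax about 1.5-fold higher for 20 mg/kg Q4W than for 10 mg/kg Q2W. The model gives 2(1 − 2^(−14/21))/(1 − 2^(−28/21)) = 2 × 0.370/0.603 = 1.23. It understates the peak, so 40% is a rough guide and the true ratio may be lower.

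**3. If all six SAP times were assayed for durvalumab**

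Cmax, tmax and AUC0-t to Day 28 could be derived. Two limits remain.

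- Extrapolated share of AUC0-∞ = 2^(−28/21) = 39.7% (39.8% when the SAP's trapezoidal rule is applied to the six times). The SAP excludes values above 30% from the summaries. The share falls below 30% only if t½ < 28 × ln 2/ln(1/0.30) = 16.1 days.
- The longest terminal interval, from 6 h to Day 28, is 28 − 0.25 = 27.75 days. The SAP flags a half-life when the interval is shorter than 2 × t½ = 42 days.

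Timing also matters. Table 6 counts hours from the start of injection. Protocol sections 10.1 and 10.2 put durvalumab at least 30 minutes later, over a standard 1 hour. The nominal 3 h draw is therefore at most 3 − 1.5 = 1.5 h after the infusion ends.

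**4. mRNA-2416 and the C2D1 value**

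Day 15 is at 14 × 24 = 336 h and C2D1 at 28 × 24 = 672 h. AUC0-t runs to the last quantifiable value, so a quantifiable C2D1 result would extend it from 168 h to 672 h across the unsampled dose at 336 h. Without C2D1, the points after Cmax are 6, 24 and 168 h if tmax is 3 h (three), but only 24 and 168 h if tmax is 6 h (two, below the minimum).

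**The case against.** The best defence is that the plan tolerates sparse durvalumab data. The endpoint is exploratory, protocol section 10.12.1 allows sampling to be reduced or stopped, and SAP section 11.5 computes parameters only where data allow. All of that is true and limits the consequence. It does not correct SAP section 11.4, which states that samples are collected when Table 6 does not schedule them. Nor does it block Cmax, which one value satisfies. The SAP's precedence clause in section 1 concerns methods and cannot supply samples.

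A reader might infer that durvalumab Cmax and AUC are beyond recovery. The documents do not support that. Arm B patients give PK serum at every Cycle 1 time, and Cmax and AUC0-t could be obtained if those tubes were assayed for durvalumab. Table 6 also has an Unscheduled mAb PK row, so the count of one refers to scheduled samples.

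A reader might also infer that a Cmax low by 60% will be reported. No text says the trough will be published as Cmax; the SAP definition merely permits it, and the size depends on an assumed model that fits the protocol's own simulation imperfectly.

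On mRNA-2416, the distortion needs a quantifiable value 14 days after the Day 15 dose, and the documents give no data suggesting one. SAP section 11.2 sets a trailing unquantifiable value to missing, and section 11.3 lets anomalous or positive pre-dose values be excluded. These safeguards are partly discretionary, so the point survives only as a conditional one.

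**Conclusion.** The inconsistency is real and worth fixing before the PK analysis. Table 6 gives one scheduled durvalumab sample and SAP section 11.4 gives six. If Table 6 governs what was drawn and assayed, durvalumab Cmax, AUC and half-life cannot be estimated as planned, and the trough could pass as the maximum at about 40% of peak (25% to 50% for assumed half-lives of 14 to 28 days, one compartment, illustrative). Even the six-time schedule would leave AUC0-∞ excluded and half-life flagged at 21 days. The effect is confined to an exploratory endpoint.

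The mRNA-2416 matter touches a secondary AUC endpoint, but only if C2D1 is quantifiable.

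**What to change.** **Durvalumab: choose one.**

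1. Restate durvalumab PK as a descriptive C2D1 trough concentration in protocol sections 7.6 and 13.4.4 (and the matching line of the protocol summary) and in SAP sections 3.2.3, 11.4 and 11.5. Remove durvalumab Cmax, tmax, AUC, λz and half-life, and record the change in SAP section 13. This costs wording only. It gives up parameters that the scheduled sample could not support.
2. If the Cycle 1 PK serum volume permits, mark those Table 6 rows mAb PK, reference durvalumab times to the infusion, and limit the parameters to Cmax, tmax and AUC0-t. This needs no additional draw times, but it costs assays and depends on sample volumes set in the laboratory manual, which is not among the documents reviewed.

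Under either option, state how the PK analysis set rule in SAP section 4.3.4 applies by analyte. It requires a baseline and a post-baseline concentration, and Table 6 has no baseline durvalumab sample.

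**mRNA-2416.** State in SAP section 11.5 that the Day 1 AUC0-t ends at 168 h and that C2D1 is summarised as a pre-dose concentration. The cost is that λz, half-life and AUC0-∞ may not be estimable in patients whose tmax is 6 h. While editing, correct the SAP's description of the Day 8 sample as pre-dose: the Schedule of Events has no dose that day, and Table 6 times it as 168 h after injection.

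### SAP 11.4: one early zero removes a time point from the only planned summary concentration plot, and missed samples after dosing may be filled in as zeros

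*SAP*

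**What the plan says.** SAP 11.2 gives the default: "Concentration values that are below the limit of quantification (BLQ) will be set to zero, with defined exceptions as follows". The exceptions narrow it. BLQ values lying between two quantifiable ones become missing, and so do trailing ones: "BLQ values following the last quantifiable concentration in a profile will be set to missing for the purposes of PK analysis". A profile with nothing quantifiable drops out: "If an entire concentration-time profile is BLQ, the profile will be excluded from the PK analysis". For absent samples the section adds: "If a pre-dose concentration is missing, these values may be set to zero".

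SAP 11.4 places the samples before the first dose, then "at 3, 6 and 24 (Cycle 1 Day 2) hours post-dose and at pre-dose on Cycle 1 Day 8 and Cycle 2 Day 1". At each nominal time the concentrations are to be "summarized using descriptive statistics by nominal time point (n, mean, standard deviation, coefficient of variation [CV], geometric mean, median, minimum, and maximum"). The geometric mean carries a restriction: "Geometric mean will not be calculated where the minimal concentration values include zero". The summary plot relies on that same statistic: "Geometric mean serum concentration by nominal time profiles by period and treatment both in linear and semi-logarithmic scale will be provided". Individual concentration plots are planned on both scales. No rule says what to plot when the geometric mean is not calculated.

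Protocol Table 6 (Section 10.13) describes the Cycle 1 Day 8 sample as taken 168 h after the injection. SAP 3.3 puts the Cycle 1 injections on Days 1 and 15, so no dose falls on Day 8.

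**The concern.** There are two linked problems.

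- **Fragile plot.** The only summary profile is drawn on a statistic that a single zero switches off. One patient whose drug level becomes quantifiable later than in the others can remove a time point for a cohort in which everyone else has a usable value. The chance of this rises with the number of patients, so the expansion cohorts are the most exposed.
- **Zeros for missed samples after dosing.** Zero is reasonable for a missing value before any drug has been given. Cycle 1 Day 8 and Cycle 2 Day 1 both come after dosing, yet under the SAP's labels the same allowance reaches them. A zero there is not a measurement. It cancels the geometric mean and also distorts the arithmetic mean that would otherwise serve as the backup.

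At stake is the reporting of mRNA-2416 concentrations (PK is a secondary objective) and durvalumab concentrations (exploratory). No primary endpoint is involved.

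**Working it through.** The plan gives no figure to reproduce, so the check traces the rules and then sizes the effect under stated assumptions.

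**1. Which zeros survive 11.2?**

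- Embedded or trailing BLQ: missing, so no zero.
- All-BLQ profile: excluded, so no zero.
- BLQ before the first quantifiable value: remains zero. At Cycle 1 Day 1 pre-dose this is expected and costs nothing. After dosing it means mainly 3 h, possibly 6 h.
- Missing sample labelled pre-dose: zero is optional. At Cycle 1 Day 1 the route is limited, because SAP 4.3.4 requires a baseline result for the PK analysis set. It remains open at Cycle 1 Day 8 (by label) and Cycle 2 Day 1.

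Two loose ends add to this. Read literally, a trailing BLQ at Cycle 2 Day 1 first becomes missing and may then, as a missing pre-dose value, become zero again. The trailing-BLQ exception is also stated for PK analysis purposes, which leaves open whether it covers the concentration summaries or only the PK parameters.

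**2. Trace on invented data.** Six patients at 3 h: 8, 5, 10, 6, 7 and one early BLQ set to 0.

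- Geometric mean under 11.4: not calculated.
- Arithmetic mean: (8+5+10+6+7+0)/6 = 36/6 = 6.0.
- Median of 0, 5, 6, 7, 8, 10: (6+7)/2 = 6.5.

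Five of six values are quantifiable. The table still describes the time point, but the plot has nothing to show there.

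**3. Chance of losing a point.** P(at least one zero) = 1 − (1 − p)^n, where p is a patient's chance of a zero at that time. Both p and independence between patients are assumptions. Cohort sizes are from SAP 4.1: 3 to 6 in escalation; 15 in the first stage of the Arm B expansion; 27 and 41 evaluable in the full Arm A and Arm B expansions.

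| n | p = 1% | p = 5% | p = 10% | p = 20% |
|---|---|---|---|---|
| 3 | 3% | 14% | 27% | 49% |
| 6 | 6% | 26% | 47% | 74% |
| 15 | 14% | 54% | 79% | 97% |
| 27 | 24% | 75% | 94% | 99.8% |
| 41 | 34% | 88% | 99% | about 100% |

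Example: 1 − 0.95^6 = 1 − 0.735 = 0.265.

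**4. Effect of a zero for a missed sample.** If k observed values have mean m, adding one zero gives mk/(k+1). With k = 5 the mean falls to 5/6 of its value, a drop of 17%. With k = 2 it falls to 2/3, a drop of 33%.

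**5. How far is zero from the expected level?** Protocol 6.5 gives a durvalumab half-life of about 21 days at doses of at least 3 mg/kg every 2 weeks. Assuming simple exponential decline, the fraction left 28 days after the first infusion is 2^(−28/21) = 2^(−1.33) = 0.40. A zero for a missed Cycle 2 Day 1 durvalumab sample would therefore stand in for a level expected to be about 40% of its starting value.

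**The case against.** The strongest reply is that the trigger is narrow and little is lost. Most BLQ values never become zeros in the summaries. Zero for a missed sample is a permission, not an instruction. The Day 8 route depends on a loose label that Table 6 contradicts. The arithmetic mean, SD, CV, median, minimum and maximum are tabulated, and individual plots are provided. Declining to print a geometric mean that includes a zero is transparent. All of this stands, and it is why the point is minor. It leaves two gaps: no fallback for the plot, and a discretionary zero after dosing that affects the arithmetic mean as well.

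A reader might go further in two ways that the documents do not support.

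- **That points vanish where exposure is lowest, so low-dose cohorts lose the early profile and high-dose cohorts keep it.** This is not shown. Late low values become missing and patients with no quantifiable value are excluded, so neither triggers the rule. A missed sample need not depend on concentration. The loss also grows with n, and the largest cohorts are the expansion cohorts, enrolled at the MTD/RDE.
- **That dose levels or arms are to be compared on the mean profile.** No such comparison is planned. The PK endpoints are Cmax and AUC, derived from individual profiles (SAP 11.5) and summarized with their own statistics (SAP 11.6).

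**Conclusion.** The point holds as a minor reporting defect with two parts.

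First, a single early post-dose BLQ set to zero removes a time point from the only summary concentration plot, and the SAP has no fallback. The mechanism follows from the text. How often it would happen is unknown, because the documents state neither a BLQ rate nor a quantification limit. The probabilities above illustrate assumed rates under independence and are not forecasts for this trial. The cancellation rule does not alter the tabulated mean or median, the individual plots, Cmax or AUC.

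Second, the allowance to set a missing pre-dose value to zero extends, by the SAP's own labels, to two samples taken after dosing. If used, it puts an invented value into the summaries, cancels the geometric mean and lowers the arithmetic mean. The durvalumab case is the clearest, given the half-life in the protocol; the 40% figure assumes simple exponential decline and is only a rough guide.

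**What to change.** In SAP 11.2, limit the zero rule for missing pre-dose values to the sample before the first dose (Cycle 1 Day 1), and state that every later missed sample stays missing. This also closes the route by which a trailing BLQ could return as zero. In the same edit, say whether the BLQ exceptions apply to the concentration summaries.

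In SAP 11.4:

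- Relabel Cycle 1 Day 8 as 168 h post-dose, to agree with protocol Table 6.
- Draw the summary profile on medians, which 11.4 already tabulates, or use the median wherever the geometric mean is not calculable. The median is zero only when more than half of the values are zero, so one zero cannot remove a point from a cohort of three or more.
- Omit zero medians from the semi-logarithmic plot, where they cannot be drawn.
- Show the number of BLQ values at each time point.

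Substituting half the quantification limit is not proposed. In the invented 3 h example it would give a geometric mean of 3.07, 4.02 or 4.51 for an assumed limit of 0.1, 0.5 or 1, against 7.0 from the five quantifiable values alone. The answer would rest on a limit that the documents do not state.

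The cost is SAP wording and a changed plotting statistic. No new data are needed, and no primary endpoint is touched.
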